7.3 Treatment Descriptors

The following convention will be used to represent treatment groups in all displays:

Table 7-1 Description of Treatment Groups

Treatment Group		Data Display	Order of Treatment Groups
Code	Description		
A	CSL112	CSL112 6g	1
B	Placebo	Placebo	2

A Total column will be displayed on select displays (such as study population tables) and will be indicated in the table mock-ups. Display columns will be in group order, that is, the left-most treatment column will be Group 1 (CSL112 6g), followed by Group 2 (Placebo), followed by a Total column for selected displays as indicated in the display mock-ups.

7.4 Multiple Comparisons and Multiplicity

There are two possible sources of multiplicity in this study: one, the planned interim analysis for efficacy; two, the inclusion of three key secondary endpoints along with the primary endpoint in the formal hypothesis testing framework.

Inflation in type I error due to interim efficacy (ie, early termination for benefit) analysis will be controlled with the use of an alpha-spending function from the Rho family, as described in [Section 4.6](#).

Issues related to multiplicity arising from testing the primary endpoint and key secondary endpoints will be addressed using the serial gatekeeping procedure [[Dmitrienko et al, 2013](#)] to control the overall experiment-wise error rate at a 1-sided 0.025 level. Three families of null hypotheses will be defined with family 1 consisting of the primary endpoint (ie, H_{01}), family 2 consisting of the 2 key secondary endpoints (H_{02} and H_{03}) and family 3 consisting of the third key secondary endpoint. The null hypothesis associated with each of these endpoints is given below:

- H_{01} : Hazard ratio (CSL112: Placebo) for time to first CV death, MI, or stroke (from the time of randomization through 90 days) ≥ 1.0
- H_{02} : Rate ratio (CSL112: placebo) of hospitalizations for coronary, cerebral, or peripheral ischemia during 90 days from the time of randomization is ≥ 1.0
- H_{03} : Hazard ratio (CSL112: Placebo) for time to first occurrence of CV death, MI, or stroke from the time of randomization through 180 days) ≥ 1.0
- H_{04} : Hazard ratio (CSL112: Placebo) for time to first occurrence of CV death, MI, or stroke from the time of randomization through 365 days) ≥ 1.0

If H_{01} is rejected at the interim analysis (ie, 1-sided $p < 0.000083$) or at the final analysis, then the hypothesis tests associated with the second family will be performed using the Hochberg procedure at a 1-sided, 0.025 type I error level. The testing will proceed from the

largest to smallest raw P value (step-up). The largest P value will be compared to a 0.025 significance level and if significant, the remaining null hypothesis will also be rejected; if not, the second P value will be compared to a 1-sided 0.0125 significance level. Testing will proceed to family 3 (H_{04}) at a 1-sided 0.025 level only if both family 2 null hypotheses, H_{02} and H_{03} , are rejected.

If the formal testing process stops with Family 1 or Family 2 due to failure to achieve statistical significance, the remaining secondary outcomes will be considered as exploratory outcomes.

8 Data Handling Conventions

Treatment assignments will be applied to clinical data at the time of the database lock. The randomization schedule and clinical data will be merged by randomization number thus matching subjects to the correct treatment assignment.

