### **3.6       Definition of End of the Clinical Study**

The end of the clinical study (ie, completion of the study at all participating study sites) will be at least 365 days after the last subject is randomized (ie, all subjects have completed the EOS Visit).

If the study is to be terminated early for reason of futility or efficacy based on interim analysis results, the following definitions would apply to subject follow-up:

- If the study is terminated early for futility, the end of the clinical study is defined as the latest date that a randomized subject has a study visit.
- If the study is terminated early for efficacy, enrollment will cease upon the announcement of the decision to stop the study. In this case, the end of the clinical study is defined as the date the last subject randomized has completed the EOS Visit.

Refer to [Section 10.3.6](#) for details regarding the 3 planned interim analyses and [Section 4.3.4](#) for procedures for subject follow-up.

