### **10.3.2.5      Multiplicity**

Issues related to multiplicity arising from testing the primary endpoint and key secondary endpoints will be addressed using the serial gatekeeping procedure [Dmitrienko et al, 2013] to control the overall experiment-wise error rate at a 1-sided 0.025 level. Three families of null hypotheses will be defined with family 1 consisting of the primary endpoint (ie,  $H_{01}$ ),

family 2 consisting of the 2 key secondary endpoints ( $H_{02}$  and  $H_{03}$ ), and family 3 consisting of the third key secondary endpoint ( $H_{04}$ ). The null hypothesis associated with each of these endpoints is given below:

- $H_{01}$ : Hazard ratio (CSL112:Placebo) for time to first CV death, MI, or stroke from the time of randomization through 90 days  $\geq 1.0$ .
- $H_{02}$ : The risk ratio (CSL112:Placebo) of hospitalizations for coronary, cerebral, or peripheral ischemia from the time of randomization through 90 days  $\geq 1.0$ .
- $H_{03}$ : Hazard ratio (CSL112:Placebo) for time to first occurrence of CV death, MI, or stroke from the time of randomization through 180 days  $\geq 1.0$ .
- $H_{04}$ : Hazard ratio (CSL112:Placebo) for time to first occurrence of CV death, MI, or stroke from the time of randomization through 365 days  $\geq 1.0$ .

If  $H_{01}$  is rejected at the interim analysis (ie, 1-sided  $P < 0.000083$ ), then the hypothesis tests associated with the second family will be performed using the Hochberg procedure at 1-sided, 0.025 type I error level. The testing will proceed from the largest to smallest raw  $P$  value. Of the 2  $P$  values, the larger will be compared with a 0.025 significance level; if significant ( $P < 0.025$ ) then the remaining null hypothesis will also be rejected; otherwise, the smaller  $P$  value will be compared with a 1-sided significance level of 0.0125. Testing will proceed to family 3 ( $H_{04}$ ) at a 1-sided 0.025 level only if both family 2 null hypotheses,  $H_{02}$  and  $H_{03}$ , are rejected.

If the formal testing process stops with family 1 or family 2 because of failure to achieve statistical significance, the remaining secondary outcomes will be considered as exploratory outcomes.

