If the observed, 1-sided  $P$  value exceeds or is equal to the significance level at the efficacy interim analysis then the study will continue until 100% of events have been accrued. In this situation, testing of key secondary endpoints will be undertaken only at the final analysis using a 1-sided type I error of 0.025.

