**Table 4** **Stopping Boundary Values**

Analysis	IF	Events	Cumulative $\alpha$ Spent	Boundary Values			
				Hazard Ratio Scale		1-Sided P-Value Scale	
				Efficacy	Futility	Efficacy	Futility
1	0.3	301	0	NA	$\geq 1.003$	NA	$\geq 0.51$
2	0.5	502	0	NA	$\geq 0.953$	NA	$\geq 0.295$
3	0.7	703	0.000083	$< 0.753$	NA	$< 0.000083$	NA
4	1.0	1004	0.025	$< 0.884$	$\geq 0.884$	$< 0.024999$	$\geq 0.024999$

IF = information fraction; NA = not applicable.

The boundaries are defined in East 6.4 to preserve 1-sided type I error at 2.5% under the assumption of a nonbinding futility rule.

In the event the efficacy stopping boundary is met at the third interim analysis, the IDMC will review key secondary endpoints, components (CV Death, spontaneous MI and stroke), and subgroups of the primary endpoint. Prior to recommending early termination of the study due to efficacy, the IDMC will ensure the presence of positive trends for key secondary endpoints and components of the primary MACE endpoint, as well as consistency across subgroups for the primary MACE endpoint. In addition to meeting the efficacy stopping boundary for the primary MACE endpoint, there will be a criterion for benefit in CV death or all-cause mortality, with details to be specified in the IDMC charter. In considering both efficacy data and safety data, an extremely compelling benefit / risk must be observed in order to recommend early stopping for efficacy.

If the study is terminated early for efficacy, a final analysis will be performed to account for data that have accrued during the conduct of the interim analysis and to test the key secondary endpoints. The results from the interim analysis where the efficacy threshold was met, as well as the final analysis, will be presented in the final clinical study report.

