10.2 Analysis of Key Secondary Endpoints

The key secondary endpoints will be analyzed based on the ITT population. The null hypothesis associated with each key secondary endpoint will be tested at the time of final analysis. The analysis will be based on CEC-adjudicated events and an assessment of concordance between the investigator-reported and CEC adjudicated events will be undertaken. Multiplicity adjustments are discussed in [Section 7.4](#).

The three key secondary endpoints and their planned analyses are given below:

10.2.1 Total number of hospitalizations for coronary, cerebral, or peripheral ischemia through 90 days after randomization

A negative binomial regression model will be fitted to the count data arising from the number of hospitalizations. This analysis will consider only those hospitalizations adjudicated by the CEC as meeting endpoint criteria. The model will include fixed effects for treatment, region, index MI type, and index MI management, age (as a continuous variable), diabetes, peripheral artery disease, and history of MI, and a term for interaction between index MI type and index MI management which correspond to the covariates in the primary analysis. The log link function will be used and the log-transformed duration of follow-up (based on the date of last MACE ascertainment) within 90 days will be included in the model to account for the variable duration of follow-up across subjects. However, if the model fails to converge then the offset statement will be excluded. The mean rate of hospitalization per 90 days will

be presented by treatment arm. A 1-sided P value for treatment comparison, the rate ratio (CSL112: placebo) and its 95% CI will be estimated from the model.

A cumulative plot of recurrent hospitalization events will be generated using a non-parametric estimator for the mean cumulative function (MCF). Nelson [[Nelson, 2003](#)] introduced the MCF as a way to summarize the average number of events occurring in a subject by time t , within a population exposed to censoring events such as losses to follow-up and termination of the study. It assumes non-informative censoring and the risk set decreases only when an individual is removed from follow-up. A supportive data listing of hospitalization data will be produced.

The SAS code for fitting a negative binomial regression model to the count data from hospitalizations is given in [Appendix 15.5](#).

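### Key secondaries are tested at the full 0.025 whichever analysis rejects H01, so the stated experiment-wise control at 0.025 can be modestly exceeded

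*SAP*

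**What the plan says.** SAP 7.4 names two sources of multiplicity, the efficacy interim and the three key secondaries. The interim is handled by a rho-family spending function (parameter 16; SAP 4.6.1.1) and the endpoints by serial gatekeeping, the stated aim being "to control the overall experiment-wise error rate at a 1-sided 0.025 level". If H01 is rejected, whether at the last look or at the interim, "then the hypothesis tests associated with the second family will be performed using the Hochberg procedure at a 1-sided, 0.025 type I error level". Family 3 (H04) is then tested at 0.025 if H02 and H03 are both rejected.

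Protocol 10.3.2.5 agrees. After an interim rejection, family 2 is "performed using the Hochberg procedure at 1-sided, 0.025 type I error level". Otherwise "testing of key secondary endpoints will be undertaken only at the final analysis using a 1-sided type I error of 0.025".

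On timing, SAP 10.2 says: "The null hypothesis associated with each key secondary endpoint will be tested at the time of final analysis". If the trial stops early for efficacy, Protocol 10.3.6.1 says "a final analysis will be performed to account for data that have accrued during the conduct of the interim analysis and to test" the key secondaries. In that case, under Protocol 3.6, "enrollment will cease upon the announcement of the decision to stop the study".

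Neither document gives H02 to H04 a spending function or a level that depends on the analysis at which H01 was rejected.

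**The concern.** The two multiplicity devices are each sound, but nothing links them. Spending controls the error for H01. Hochberg with serial gatekeeping is a standard choice for a single fixed analysis with positively dependent endpoints. In this design, H01's interim statistic also decides which dataset a secondary is tested on: the shortened trial or the complete one. A secondary that correlates with the primary tends to look favourable by chance in exactly those trials that stop early. It can also be rejected at the full 0.025 in trials that run to completion. The union of these two events can exceed 0.025 even though only one of them can occur in any one trial.

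H02 to H04 are the only secondaries with formal testing status, and SAP 10.1.3 describes a single pivotal trial supporting registration. The stated error rate for these claims should therefore be one that the design delivers.

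**Working it through.** **The plan's own figures reproduce.**
- Interim alpha: 0.025 × 0.7^16 = 0.0000831, so c1 = 3.766 and the boundary hazard ratio (HR) is exp(−2 × 3.766/√703) = 0.753.
- Final boundary: P(Z at 70% > c1 or Z at 100% > c2) = 0.025 with correlation √0.7 gives c2 = 1.95997, nominal level 0.024999, HR 0.884.
- Interim crossing at HR 0.80: drift θ = −ln(0.80) × √1004/2 = 3.535, and 3.535 × √0.7 = 2.958. P(Z > 3.766 − 2.958) = 0.21.
- Power with the stated futility bounds is 91.9%.

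All agree with SAP 4.5 and 4.6.1.1.

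**Error for one true-null secondary under the written rule.** Let Zp be the primary statistic, with drift θ√0.7 at the interim and θ at the end. Let Zs be the secondary statistic, with mean 0. Let t be the secondary's information at an early stop as a fraction of the full trial, and r the correlation between the endpoints at equal information.

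E = P(Zp,0.7 > c1 and Zs,t > 1.96) + P(Zp,0.7 ≤ c1 and Zp,1 > c2 and Zs,1 > 1.96)

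Here corr(Zp,0.7, Zs,t) = r√(0.7/t), corr(Zp,0.7, Zs,1) = r√0.7 and corr(Zp,1, Zs,1) = r. The non-binding futility looks are ignored.

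**Information at an early stop.** The interim counts only subjects enrolled at least 90 days before cutoff (SAP 4.6.1.1), so about 3 further months of enrolment already exist. With uniform enrolment over 38 months, t = 0.70 + 3/38 = 0.78. With 2 more months before enrolment ceases (assumed), t = 0.70 + 5/38 = 0.83. After an efficacy stop the study ends when the last randomized subject completes the EOS visit (Protocol 3.6), so everyone enrolled is followed. I take 0.78 to 0.90 as the range. Neither t nor r is given in the documents.

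**Results**, maximised over the true primary HR:

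| t | r = 0.6 | r = 0.84 | r = 0.95 | range at HR 0.80 |
|---|---|---|---|---|
| 0.78 | 0.0268 | 0.0283 | 0.0296 | 0.0262–0.0270 |
| 0.83 | 0.0263 | 0.0274 | 0.0283 | 0.0261–0.0265 |
| 0.90 | 0.0257 | 0.0263 | 0.0267 | 0.0257–0.0259 |

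The maxima fall at primary HR 0.81 to 0.85, between the design value of 0.80 and the minimally relevant value of 0.85. At t = 1 the maximum is exactly 0.025, so the shortened dataset is the cause. If H01 is also null, the error is about 0.015 (r = 0.9, t = 0.83).

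**Effect of Hochberg.** A family-2 endpoint is tested at 0.025 only if the other P value is also significant at 0.025. Otherwise its level is 0.0125. At t = 0.83, with the other endpoint assumed independent:
- About 80% power for the other endpoint: at most about 0.025.
- 90% power: about 0.0255 to 0.0264 at the higher correlations.
- 99% power: about 0.027 to 0.028 at the higher correlations.

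The table is therefore the limit as the other null becomes certain to be rejected.

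**Effect of the CV-death condition** (SAP 4.6.1.1). With CV death assumed to be 20% to 40% of primary events, r = 0.9 and t = 0.83, the maximum is about 0.026 to 0.0275, before any Hochberg reduction.

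**The case against.** The strongest defence has four parts.

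1. **Each secondary is tested once, at a final analysis.** This is correct. A reader might infer two looks at 0.025 from the interim-or-final wording, but SAP 10.2 and Protocol 10.3.6.1 rule that out. The defence does not restore control, because the final analysis after an early stop is of a smaller trial selected by the correlated primary result.
2. **The excess is small and conditional.** This is also correct. A reader might quote figures for testing on the interim data alone (t = 0.70): 0.0277 to 0.0327 for r = 0.6 to 0.95, or 0.037 at r = 1. The documents do not plan that test, because overrun is built in. Hochberg and the CV-death condition reduce the excess further. The CV-death rule governs the committee's stopping recommendation, however, whereas SAP 7.4 defines interim rejection by P < 0.000083 alone.
3. **Very high correlation is hard to reconcile with a true null for H03.** Suppose r² is the share of day-180 events that fall in the first 90 days. At r = 0.95 and primary HR 0.86, an exactly null H03 needs a day 91–180 HR of exp(0.9025 × 0.1508/0.0975), about 4. At r = 0.84 and HR 0.84 it needs exp(0.7056 × 0.1744/0.2944), about 1.5. The top of the range is therefore unlikely for H03. The lower and middle parts stand.
4. **The plan does not use the term strong control.** True. If the claim covers only the case where every null holds, the gate satisfies it. A gatekept claim on secondaries matters only once H01 is false, so that reading would empty it.

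**Conclusion.** The control statement in SAP 7.4 and Protocol 10.3.2.5 is wrong as written, by a modest amount. For one true-null key secondary with H01 false, the worst case is about 0.026 to 0.030, given secondary information of 0.78 to 0.90 at an early stop and correlation of 0.6 to 0.95 (both assumed). At the design HR of 0.80 it is 0.0257 to 0.0270. These are upper limits that assume the other family-2 null is rejected. If that endpoint has only about 80% power, the figure is about 0.025 or below. For H04, both H02 and H03 must be rejected first.

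There is no excess if the 70% look is skipped, as both documents allow, if the trial runs to full size, or if H01 is also null. A reader should not infer that the primary test is affected: its boundaries reproduce and hold.

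**What to change.** Prespecify for families 2 and 3 a level-0.025 group-sequential boundary that depends on the analysis at which H01 is rejected. Within Hochberg, use the boundary level and half of it in place of 0.025 and 0.0125. Test H04 at the boundary level. Two options:

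- **O'Brien-Fleming type:** with 80% information at an early stop, about 0.012 after the stop and 0.021 at the final analysis. The single-secondary maximum is then 0.0218 at r = 0.95.
- **Pocock type:** about 0.016 at both times, calculated at 70% information. The maximum is 0.0243 even at r = 1.

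State how information is measured for each secondary. The documents give no planned totals for H02 to H04; the fraction of planned subjects enrolled is a workable substitute when all are followed. Confirm the combined Hochberg procedure by simulation.

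Alternatively, keep 0.025 and replace the control claim with the computed maximum error and its assumptions.

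Cost: a change to the SAP text and the matching protocol section, plus some power. With the O'Brien-Fleming-type boundary at 80% information, a secondary with 90% full-trial power keeps about 89% at the final analysis. After an early stop its power falls from about 83% to 74%.

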8.1 Missing Data

8.1.1 Missing Baseline Covariates

Missing values for baseline risk factors including diabetes mellitus, peripheral artery disease (PAD), or prior MI can be expected to occur in a small subset of subjects enrolled in the study. These risk factors are included in the proportional hazards regression model for the analysis of the primary and other endpoints as independent covariates. To prevent the casewise deletion of records due to missing baseline covariates, a single imputation from the Fully Conditional Specification (FCS) under a generalized logit distribution (appropriate for non-ordered categorical data) and missing at random assumption will be obtained [White et al, 2011]. The imputation model will include all the covariates considered in the analysis of the primary endpoint but not the treatment or outcome. The inclusion of a term for interaction between index MI type and management type will be omitted if cells with zero events are encountered as it could result in failure to fit the model. The completed dataset will be saved and utilized for all planned analyses as applicable. The SAS code fragment is shown in [Appendix 15.5](#).

8.1.2 Imputation of Non-Date Missing Data

As per the protocol, subjects are to be followed for 365 days regardless of compliance with treatment or protocol; however missing efficacy event data can occur if a subject withdraws

consent for additional post-discontinuation assessments. Imputation of missing event data when subjects are non-administratively censored is described in [Section 10.1.1](#).

If the investigator assessment of causal relationship to study treatment for adverse events (AEs) and serious adverse events (SAEs) is missing then the adverse events will be assumed to be “related”. There will be no other imputation for missing data other than as described in Section 8.1.3 for partial dates and times.

8.1.3 Imputation of Partial Dates

Partial dates will be imputed dates for the purpose of slotting medications, adverse events, and other data into distinct study periods as well as for sorting in data listings. They will not be used to derive study day, duration (eg, duration of adverse events), or elapsed time variables. In addition, imputed dates are not used for deriving the last contact date for time to event variables.

Partial date imputation will follow Analysis Data Model (ADaM) conventions. The ADaM approach is to populate the numeric date variables with the imputed date and add a flag variable to the dataset that indicates the level of imputation.

The flag variable can contain the values: blank, 'D', 'M', 'Y'.

Blank: indicates that no imputation was done

D = 'Day': indicates that the day portion of the date is imputed

M = 'Month': indicates that the month and day portions of the date are imputed

Y = 'Year': indicates that the entire date (year, month, and day) is imputed

Algorithms for imputing partial dates for AE and concomitant medications are given below.

Imputations in the adverse events dataset are used for slotting events to the appropriate study time periods and for sorting in data listings. They will not be used to calculate duration of AEs. If an AE start or end date is missing, then the duration of the AE will be set to missing.

Adverse Events

Date	Missing Element	Rule
Start Date	day, month, and year	
 Do not impute completely missing AE start dates The AE will be deemed treatment-emergent if the AE end date does not indicate that the AE ended prior to study treatment start date
	day, month only	
 If the study treatment start date is not missing: 
 If the year of AE start date is the same as the year of study treatment start date 
 If the AE end date indicates the AE ended prior to study treatment start date then set AE month and day to January 1 Otherwise set month and day of AE start date to study treatment start date If the study treatment start date is missing then set month and day of AE start date to January 1.
	day only	
 If the study treatment start date is not missing: 
 If the month and year of AE start date is the same as the month and year of study treatment start date 
 If the AE end date indicates the AE ended prior to study treatment start date then set day of AE start date to the 1st of the month Otherwise set day of AE start date to study treatment start date If the study treatment start date is missing then set day of AE start date to 1st day of the month of AE start date.
End Date	any date element	No imputation for completely or partially missing AE end dates; as applicable, report the AE as ongoing and the AE duration as missing.

Concomitant Medications

Medication start and end dates will be imputed as necessary to define the time period of usage through study Day 90 or the end of study. Imputed dates will be recorded in the concomitant medications analysis dataset with a flag variable as previously described to indicate the imputed portion(s) of date.

Concomitant Medications

Date	Missing Element	Rule
Start Date	day, month, and year	Completely missing medication start dates will not be imputed and all values that depend on this date will be set to missing 
 Concomitant medication if medication end date is on or after treatment start date
	day, month	
 If study treatment start date is missing or medication end date is before treatment start date then day and month portion of the medication start date = January 1. If study treatment start date is not missing & medication end date is on or after treatment start date then medication start date = treatment start date
	day	
 If study treatment start date is not missing: 
 If the month and year of the medication start date is the same as the month and year of treatment start date then 
 If the medication end date indicates the medication ended prior to the study treatment start date then set the day portion of medication start date to the 1st of the month Otherwise set the day of the medication start date to the day of the study treatment start date Otherwise set day of medication start date to the 1st of the month
End Date	day, month, and year	Completely missing concomitant medication end dates will not be imputed; all values that depend on this date will be set to missing 
 The medication will be deemed to be concomitant and ongoing
	day, month	If the medication partial end date contains the year only, then set medication end date to the earliest of [December 31 or the date of the last safety assessment or death up to day 90 in the study].
	day	If the partial medication end date contains month and year, then set the day of the medication end date to the earliest of the last day of the end month reported, the last safety assessment completed or the date of death up to day 90 in the study]

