### **8.5.3 Visits 7, 8, 9, 10, and 11 (Follow-up Period)**

Visit 7 and Visit 10 assessments may be conducted either by telephone contact or face-to-face at the study site. Visit 8, 9, and 11 assessments should be conducted face-to-face at the study site.

- Concomitant medication review of all treatments for ACS including the dose, route of administration, and frequency must be collected and monitored for change through to the EOS (Day 365). Note: All other concomitant medications taken or administered during the study will be collected through Visit 8 (Day 90), or beyond in the event of an SAE, or AEs considered related to investigational product, leading to discontinuation of investigational product, and / or leading to withdrawal of consent during the study.
- MACE endpoint assessment (all visits).
- Body weight (Visits 8, 9, and 11).
- Lifestyle adherence assessment (Visits 8, 9, and 11).
- AE monitoring (Visits 7 and 8). Note: AEs considered related to investigational product, leading to discontinuation of investigational product, and / or leading to withdrawal of consent during the study are also to be collected at Visits 9, 10, and EOS.
- AEs related to investigational product / SAE monitoring (all visits).
- EQ-5D-3L assessment (Visit 8).

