Any medication that started on or prior to the date of first infusion and the end date is either after the date of first infusion or missing (implying the medication is ongoing) is defined as a baseline medication.

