9.4 Prior and Concomitant Medications

The ITT Analysis Set will be used for describing medication usage during the study. Prior ACS-related medications taken by subjects in the 4 weeks before screening will be collected in a targeted manner. The number (%) of subjects receiving each medication of interest will be summarized.

Medication usage from the time of informed consent through 90 days from randomization will be captured. Medications intended to diagnose or treat SAEs will be captured through the end of study. All medications will be coded using the WHO Drug coding dictionary and summarized to show the number and percentage of subjects taking concomitant medications. Anatomical Therapeutic Chemical (ATC) classification Level 1 (Body System) information will be included in the dataset created but will not appear on the listing or summary.

Medications will be grouped by ATC code and summarized in alphabetical order by generic

term within ATC code. Subjects with multiple instances of the same medication will be counted once in the summary table(s).

The following output will be generated:

- Summary of Concomitant Medications through 90 days
- Summary of Concomitant Medications through End of Study
- ACS-related concomitant Medications of Interest including:
 - Aspirin
 - P2Y12 anti-platelets
 - PCSK9 inhibitors (PCSK9i)
 - Beta-blockers
 - ACE-I or ARB
 - Statins will be categorized as high, moderate, or low intensity, and none
 - Non-statin lipid-modifying agents

The number (%) of subjects receiving aspirin, statins, and P2Y12 inhibitors will be presented at study days 90, 180, and 365 for ascertaining the degree of compliance with evidence-based therapy; reasons for not doing so will be summarized with number (%) of subjects presented for each medication and reason.

Identification of ACS-related Medications:

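### Two partial-date rules for concomitant medication in SAP 8.1.3 can override the year that the site recorded; the effect is confined to descriptive, and possibly exploratory, medication outputs

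*SAP*

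**What the plan says.** **Purpose.** SAP 8.1.3 says medication dates are imputed to define usage both through Day 90 and through end of study. Only one set of rules is given for both.

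**Starts, day and month missing.** If the "medication end date is on or after treatment start date then medication start date = treatment start date". The recorded year is not consulted. Two neighbouring rules in the same section do consult the recorded date parts. The adverse-event rule first asks "If the year of AE start date is the same as the year of study treatment start date", and the day-only medication rule compares month and year and otherwise uses the first of the month.

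**Stops.**
- Year only: the "earliest of [December 31 or the date of the last safety assessment or death up to day 90 in the study".
- Month and year: the day is set to the earliest of the month end, "the last safety assessment completed or the date of death up to day 90 in the study".
- Fully missing: not imputed. "The medication will be deemed to be concomitant and ongoing".

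**Where the dates go.** SAP 8.3.2 slots starts and stops as BEFORE, DURING or AFTER therapy. It defines a baseline medication by "Any medication that started on or prior to the date of first infusion", with the stop later than first infusion or missing. SAP 9.4 says the numbers on aspirin, statins and P2Y12 inhibitors "will be presented at study days 90, 180, and 365 for ascertaining the degree of compliance with evidence-based therapy". Protocol 8.5.3 says treatments for ACS "must be collected and monitored for change through to the EOS (Day 365").

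**The concern.** An imputation rule should fill in what is missing and leave alone what was recorded. Both year-only rules can fail that test. The start rule can move a drug into a different calendar year from the one the site entered. The stop rule can do the same, because a limit suited to medication collected only to Day 90 is applied to ACS drugs collected to Day 365.

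At stake is the description of background therapy: which drugs count as baseline, which count as started during treatment, and possibly who is shown as still on evidence-based therapy at Day 180. Date-derived exploratory tables could also be touched. Examples are the creatinine summary by ACE inhibitor or ARB use during active treatment (SAP 11.6.2.1) and the subgroups by medication at randomization (SAP 10.1.2).

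**Working it through.** The plan states no figure to reproduce, so the check applies the rules as written. Study day is date minus first-infusion date plus 1 (SAP 8.2.2). On-therapy ends one week after the last infusion (SAP 8.3.1), about Day 29. A safety assessment is assumed on Day 90.

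**1. Start rule.** First infusion 15 Nov 2020, stop 1 Sep 2021, start recorded by year only. The imputed start is 15 Nov 2020 in every case.

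| Recorded year | Start relative to therapy: true | Imputed | Baseline: true | Imputed |
|---|---|---|---|---|
| 2015 | BEFORE | DURING | yes | yes |
| 2021 | AFTER | DURING | no | yes |

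For 2021 the earliest possible start is 1 Jan 2021, which is Day 48 and so past the on-therapy period. If first infusion falls so late in December that on-therapy runs into January, DURING could be right by chance, but baseline is still wrong. For a recorded year equal to the infusion year, the record cannot settle the order, so no contradiction arises.

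**2. Year-only stop rule.**
- First infusion 1 Jul 2020, so Day 90 is 28 Sep 2020. A stop recorded as 2021 becomes min(31 Dec 2021, 28 Sep 2020) = 28 Sep 2020, which is before the recorded year.
- First infusion 15 Nov 2020, so Day 90 is 12 Feb 2021. A drug started on Day 120 (14 Mar 2021) with a stop recorded as 2021 gets a stop of 12 Feb 2021, 30 days before its start.
- Largest displacement within the 365-day follow-up: 365 − 90 = 275 days.

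**3. Month-and-year stop rule.** The line can be read in two ways. If the Day 90 limit covers the safety assessment, then with first infusion 15 Nov 2020 a stop recorded as Aug 2021 becomes 12 Feb 2021, against the recorded month. If only the day may be set, or the limit applies only to death, the stop stays in August 2021.

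**4. Enumeration.** All 366 first-infusion dates in 2020 were crossed with all 289 true stop days from Day 91 to Day 379, giving 366 × 289 = 105,774 cases. With the cap, the last assessment is Day 90; without it, Day 379. The entries are shares of partial-date stops with wrong status, not shares of subjects.

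| Stop known by | Rule | Wrong at Day 180 | Wrong at Day 365 |
|---|---|---|---|
| Year | cap at Day 90 | 69.2% | 5.2% |
| Year | last contact | 27.0% | 59.2% |
| Month and year | cap, if it applies | 69.2% | 5.2% |
| Month and year | last contact | 5.1% | 5.1% |

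With the cap, the 69.2% is 200/289: every stop on Days 180–379 shows as off drug at Day 180. The 5.2% is 15/289: only stops on Days 365–379 are wrong at Day 365. The capped year-only date contradicts the recorded year in 39.6% of cases. No case loses concomitant status or its AFTER label for the stop, because Day 90 is later than both treatment start and about Day 29.

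**The case against.** The strongest reply has four parts.

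**The link to the adherence table is not stated.** SAP 8.1.3 limits imputed dates to slotting into study periods and sorting listings, and bars their use for study day, duration or elapsed time. The protocol also has sites record departures from evidence-based therapy, and the reasons, directly in the eCRF (Protocol 7.2.1 and 8.1.1.3). The Day 90, 180 and 365 table may rest on those entries. This stands, so the Day 180 effect can only be stated conditionally.

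**The month-and-year line may not cap anything.** Read literally, it sets only the day. This also stands: the clear case is the year-only stop.

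**Derivations live in separate dataset specifications (SAP 8.2).** True, but those should implement the SAP. A specification that silently departs from a stated rule would itself need correcting.

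**The outputs are descriptive and the rules ignore treatment arm.** This stands, and it limits the weight of the point.

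A reader might infer more: that adherence at both Day 180 and Day 365 is wrong, that baseline use is wrong generally, or that the cap puts stops in the wrong study period. The documents do not support these. A stop on Days 91–364 is correctly off drug at Day 365 even when capped. Drugs from an earlier year remain baseline. The cap changes no concomitant or end-relative category.

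**Conclusion.** The year-only start rule and the year-only stop rule are wrong as written, in a small way. Followed exactly, the start rule makes a drug recorded as started in a later year a baseline medication, and usually DURING rather than AFTER. It also moves a drug from an earlier year from BEFORE to DURING. The stop rule can give a date before the recorded year or before the drug's start. The month-and-year stop line is ambiguous rather than wrong.

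The size cannot be fixed from the documents, because the number of partial dates is not given. Purely as an illustration, suppose 20% of subjects stop a P2Y12 inhibitor between Day 181 and Day 365, and 5% to 20% of those stops are partial dates that the rule caps. Day 180 use would then be understated by 0.20 × 0.05 = 1 to 0.20 × 0.20 = 4 percentage points. This holds only if the table uses imputed dates. Both inputs are assumptions, and the capped share is smaller if the month-and-year line does not cap. The enumeration shares assume stop days spread evenly over Days 91–379.

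The effect is limited to descriptive medication summaries and possibly exploratory tables or subgroups. No between-arm bias is shown, and no primary or key secondary test uses these dates.

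**What to change.** In SAP 8.1.3:

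1. **Year-only starts.** Use the treatment start date only if the recorded year equals the treatment-start year; otherwise use 1 January of the recorded year. The second branch must be written out, because the adverse-event rule is silent when the years differ.
2. **Stops.** Keep the Day 90 limit for the through-Day-90 summary only, and say whether it applies to the assessment or just to death. For end-of-study use, set month-and-year stops to the earliest of month end, last contact or death.
3. **Guard.** Never impute a stop that contradicts a recorded month or year, or that precedes the drug's start.
4. **Year-only stops at Day 180 and Day 365.** Show status as unknown, or give both bounds. Simply replacing the cap with last contact is not enough: it would raise wrong status at Day 365 from 5.2% to 59.2% of such stops in the enumeration.

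In SAP 9.4, state whether the Day 90, 180 and 365 table is derived from imputed dates or from direct eCRF entries.

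The cost is a few lines of SAP text and a small programming change. No new data are needed.
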